1.3 Do you need funding from Assiut Medical School Grants Office?

Yes No (If no, skip and delete Part 4)

Mention other sponsoring agent(s) if any:no.....

Part 2: Research Details

**Faculty of Medicine
Institutional Review Board (IRB)**

2.1 Background (Research Question, Available Data from the literature, Current strategy for dealing with the problem, Rationale of the research that paves the way to the aim(s) of the work). **(200-250 words max.)**

Hyperuricemia is defined by serum uric acid concentration greater than 7

mg/dl in men and 6 mg/dl in women. Uric acid is the end product of purine catabolism and is excreted in the urine. Uric acid can serve as an inflammatory factor and is attributed to bring about endothelial dysfunction.¹ . Various studies have shown that hyperuricemia can cause various damages like the arteriopathy of preglomerular vessels, impaired auto-regulation, glomerular hypertension, endothelial dysfunction and microvascular disease² .

Diabetic nephropathy (DN) is a progressive kidney disease caused by the damage to the capillaries in the kidneys' glomeruli. In DN the progression of kidney damage can be partially halted but is irreversible and cannot be completely halted or reversed

Persons who have diabetes in addition to chronic kidney disease have a ~50% higher risk of end stage renal disease (ESRD) and death than those at a similar level of estimated glomerular filtration rate³.

Diabetes mellitus (DM) is a chronic disease that occurs either when the pancreas does not produce enough insulin or when the body cannot effectively use the insulin it produces. The prevalence of diabetes is swiftly increasing over the globe at an alarming rate. Diabetes mellitus is a heterogeneous group of metabolic disorders characterized by chronic hyperglycemia with disturbances of carbohydrate, fat and protein metabolism resulting from defects in insulin secretion, insulin action or both⁴.

The metabolic changes associated with diabetes mellitus further lead to pathophysiological changes in multiple organ system which are responsible for various acute and long term complications of diabetes mellitus. Among the microvascular complications, kidney is the organ which is most seriously and commonly affected⁵.

The natural history in the development of diabetic nephropathy (DN) includes glomerular sclerosis, intra-glomerular hypertension, hyperfiltration, intermittent microalbuminuria and finally frank proteinuria. If microalbuminuria stage remains unchecked and uncontrolled, it culminates in end stage renal disease⁶.

**Faculty of Medicine
Institutional Review Board (IRB)**

Diabetic nephropathy (DN) is the leading cause of end-stage renal disease

(ESRD) in the world. Current treatment methods, with better control of glycemia and blood pressure, including renin-angiotensin system blockade (RASB), appear to have slowed the DN progression rate but have not substantially decreased the annual incidence of new DN ESRD cases. Thus, new treatment targets are needed ⁷.

Uric acid serves as an independent biomarker of hypertension, diabetes mellitus, obesity, and renal disorders. Several studies indicate that uric acid has some role in type 2 diabetes mellitus, since the hyperglycemia was shown to correlate with the development of renal dysfunction in type 2 diabetes⁸.

The pathogenesis of diabetic nephropathy is complex and still not fully clarified. Uric acid has been associated with renal disease, even though hyperuricemia may be a marker of or by itself be responsible for microvascular disease in diabetes. In patients with diabetes, serum uric acid early in the course of diabetes is significantly, and independent of confounders, associated with later development of persistent macroalbuminuria. Therefore, uric acid may be a novel and important player in the pathogenesis of microvascular complications in diabetes^{9 10}.

The observed hyperuricemia in DN could be explained by several mechanisms that may operate singly or in combination. There are two possibilities of increase in blood uric acid levels. It could be increased production or decreased excretion of uric acid. Higher serum uric acid in DN is most likely due to abnormality in uric acid excretion. Hyperuricemia may result from increased net tubular reabsorption¹¹.

Hyperuricemia is seen when kidney function declines. Whether elevated uric acid (UA) levels play a role in the initiation and progression of kidney disease is a subject of a great debate¹².

Finally, small clinical trials using allopurinol to lower UA levels provide weak, but potentially promising, evidence that lowering UA levels may retard the progression of CKD.

In this study, we will study the evidence of the association of hyperuricemia and Diabetic Nephropathy in T2DM .

2.2 Aim(s) of the Research (100 words max):

This study aim is to evaluate whether treatment of hyperuricemia affects renal disease progression in patients with Type II (T2DM) diabetes mellitus or not.

2.3 Research Area (Faculty Research Plan). Choose one and delete the rest.

3

Introduction of evidence-based, cost effective management strategies in common health problems.

2.4. Research Methods and techniques:

2.4.1- **Type of the study:** Case-Control Study (Randomized Controlled Trial).

Randomization: patients fulfilling inclusion criteria will be randomized to two groups.

A computer-generated random-number table was used for allocation of individuals to the

study drug and placebo in a 1:1 ratio.

Allocation concealment: Assignment will be done by sequentially numbered , otherwise identical , sealed envelope with a written code designated the assigned group.

2.4. 2- Study Setting: Department Internal Medicine, Nephrology Unit, Faculty Of Medicine, Assiut University.

2.4. 3- Study subjects: The study will include two groups:

- Hyperuricemic group will take placebo pills (placebo group).
- Hyperuricemic group will be treated with uric acid lowering drug (febuxostat 80 mg once daily for 6 months).

The study will evaluate whether treatment of hyperuricemia affects the progression of chronic kidney disease in patients with diabetic nephropathy in T2DM and stage 3 CKD by follow up of eGFR of the two groups after 6 months .

a. Inclusion criteria: Patient population will include both males and females above the age of 18 years with T2DM and Diabetic Nephropathy stage 3 CKD (eGFR: 31-59).

b. Exclusion criteria:

- Patients with history of hypothyroidism, alcoholism, urinary tract infections, glomerulonephritis, myeloproliferative disorders and gout “as gout is a common inflammatory arthropathy characterized by painful and swollen joints resulting from precipitating uric acid crystals but hyperuricemia is commonly asymptomatic” or on drugs capable of inducing Hyperuricemia

will be excluded from the study.

- Any patient will develop acute kidney injury episode at any time of the study will be excluded from the study.
- Patients with uncontrolled hypertension will be excluded from the study.

c. Sample Size Calculation:

The required sample size was calculated using G Power 3.1.9.2 software for sample size calculation (Heinrich Heine Universität, Düsseldorf, Germany), setting α -error probability at 0.05, power (1 – β error probability) at 80% and effect size (w) at 0.43. The effect size (w) was calculated has been calculated according to data obtained from previous study (Sircar et al., 2015) where the mean of GFR in the group received Febuxostat Group was 46.7 ± 18.1 and in the placebo group the mean was 42.2 ± 11.5 . The number of participants needed to produce a statistically acceptable figure will be 87 patients in each group. Assuming a drop- out rate of 10%, this will make sample size 96 and the figure will be rounded to 100 per each group¹³.

So, the study will include 2 groups of 100 patients for each group.

2.4.4 –Study tools (in detail, e.g., lab

methods, instruments, steps, chemicals, ...):

Every patient will be subjected to

1. Full history with specific attention to:

- Special habits.
- Duration of diabetes.
- Therapeutic history.
- Past history.
- Complications of diabetes.

2. Full physical examination.

3. Investigations : : At the beginning of the study all patients will be investigated for: serum uric acid, HbA1c and renal function tests including creatinine clearance. MDRD formula will be applied for the calculation of eGFR.

4. Intervention: One of the 2 groups is the drug group will be treated with febuxostat 80 mg tablets once daily for 6 months and cardiac patients will be excluded from this group. the other group will take placebo pills (placebo group).

5. Follow up : eGFR will be done for Assessment of the outcome of the intervention after 6 months.

2.4.5 –**Research outcome measures:**

a. Primary (main):

To detect effect of treatment of hyperuricemia on eGFR as an objective criterion for assessment of progression of diabetic nephropathy in patients with T2DM.

b. Secondary (subsidiary):

To decrease progression of diabetic nephropathy as one of the most common and life-threatening complications of diabetes.

2.5-Data management and analysis:

Data collection

Data will be collected as **data sheets** from the clinical interpretation of the patient presentation and from the recent medical records of the patients which have the full histories and examination

Computer software

Data will be processed and analysed using SPSS software.

Statistical tests

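### The protocol uses a placebo but states no blinding, leaves open who can read the group code in the envelope, and contains an exclusion that only someone who knows the arm can apply

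*Combined protocol and SAP*

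**What the plan says.** Section 2.4.1 describes a computer-generated random list allocating individuals to "study drug and placebo in a 1:1 ratio". Concealment is by sequentially numbered, identical envelopes, each a "sealed envelope with a written code designated the assigned group". The section ends there. Only the envelopes are called identical; the control is described simply as placebo pills (sections 2.4.3 and 2.4.4).

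Two exclusion rules bear on the point:

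- Section 2.4.3 b, both arms: "Any patient will develop acute kidney injury episode at any time of the study will be excluded from the study". No definition and no blinded adjudication is given.
- Section 2.4.4 item 4, febuxostat arm only: "cardiac patients will be excluded from this group". This rule is not in the common exclusion list of section 2.4.3 b.

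The outcome is a single 6-month eGFR by the MDRD formula, which section 2.4.5 presents as "eGFR as an objective criterion for assessment of progression of diabetic nephropathy". Data are taken "from the clinical interpretation of the patient presentation and from the recent medical records of the patients" (section 2.5). The analysis is a t test or ANOVA, with no stated analysis set or missing-data rule. Double blinding is mentioned only in the title of a cited trial (section 2.6, reference 14).

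**The concern.** A placebo protects the comparison only if the people making decisions during follow-up cannot tell who receives it. eGFR is a laboratory value, so biased reading of the outcome is not the main risk. Two other routes remain open:

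- **Who reaches the 6-month value.** An acute kidney injury episode removes a patient from the study, and what counts as an episode is left to judgement. Withdrawals for other reasons have no rule at all.
- **What else patients receive.** No co-treatment rule is given, while section 2.1 says that better control of glycaemia and blood pressure appears to have slowed progression.

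If the people deciding these matters know the arm, their decisions can differ between arms. Part of an observed eGFR difference could then arise without any drug effect.

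**Working it through.** **Does the plan keep the arm hidden?** The plan gives no figure here, so the first step is to set its provisions side by side.

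1. The envelope code marks a group. It is not described as a patient or container number. Its reader and the holder of its key are not named.
2. The cardiac rule applies to one arm. If it is applied after randomisation, a cardiac patient removed under it was on febuxostat and one who stays is on placebo. If it is applied before, every cardiac patient in the trial is on placebo, and those patients' allocation is not random.
3. Section 2.4.4 item 1 has a full history, including past history, taken from every patient. Staff therefore know who is cardiac, and the rule reveals those patients' arm whoever applies it.
4. If staff also see a group label such as A or B, one cardiac patient whose arm is revealed decodes the label, and with it the arm of every patient who carries it.

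**How large could selective exclusion be?** Inputs from section 2.4.3 c: 100 patients per arm; means 46.7 and 42.2, so the planning difference is 46.7 − 42.2 = 4.5; SDs 18.1 and 11.5, so the pooled SD is √((18.1² + 11.5²)/2) = 15.16.

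Assumptions not in the documents: the drug has no effect; k drug-arm patients lying D units below their arm mean are removed; similar placebo patients are kept; the SD is unchanged by the removal.

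- Shift in the drug-arm mean: k × D / (100 − k)
- Standard error of the difference: 15.16 × √(1/100 + 1/(100 − k))
- With z = shift / standard error, two-sided type I error: 1 − Φ(1.96 − z) + Φ(−1.96 − z)

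| k | D | Shift | Share of 4.5 | Standard error | z | Type I error |
|---|---|---|---|---|---|---|
| 2 | 10 | 20/98 = 0.20 | 5% | 2.16 | 0.09 | 5.1% |
| 5 | 15 | 75/95 = 0.79 | 18% | 2.17 | 0.36 | 6.5% |
| 10 | 20 | 200/90 = 2.22 | 49% | 2.20 | 1.01 | 17.2% |

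For the middle row: 1 − Φ(1.597) + Φ(−2.323) = 0.055 + 0.010 = 0.065.

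**The case against.** A reader might infer that the envelope tells staff the arm and that the cardiac rule confirms it. The documents do not support that. The code could be a masked label with its key held elsewhere, and the cardiac sentence does not mention the envelope. An unblinded third party could apply the rule, so the person who knows the arm need not be the one who decides on acute kidney injury, withdrawal or co-treatment. The sentence may even be a loosely worded general eligibility criterion. A blinding statement on the title or consent pages, which were not available for this review, cannot be ruled out.

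All of this stands as a limit on the claim. It does not show that decisions are protected: no third party or key holder is named, and a third party would not stop staff who know the cardiac history from working out those patients' arm.

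Two further objections are fair. The numerical illustration rests on assumed inputs, and its middle case is only about 0.36 standard errors. Also, excluding patients for an event during follow-up can bias the comparison even under perfect blinding, because the drug itself may change who has the event. Blinding does not cure that, and the one-arm cardiac rule likewise makes the arms non-comparable in its own right. These are separate defects.

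**Conclusion.** The point holds as a gap in protection, not as proof that staff are unblinded or that bias will occur. As written, the placebo does not ensure that the decisions determining who contributes a 6-month eGFR, and what else patients receive, are made without knowledge of the arm. The firmest evidence is the one-arm cardiac exclusion; the group code adds to it if staff can see the label.

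The size is not fixed by the documents. Under the assumed scenarios the effect runs from negligible to about half the planning difference. It requires removals that are one-sided and concentrated in patients with low eGFR. The plan should be changed because the remedy is cheap, not because a large bias has been demonstrated.

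**What to change.** 1. Replace the group-coded envelope with febuxostat and look-alike placebo in identical containers numbered by patient from the existing random list. Someone not involved in care or analysis, for example the pharmacy if available, holds the list until database lock.
2. State that patients, treating staff and the analyst are blinded, and that every exclusion and withdrawal is decided and recorded, with its reason, before any code is opened.
3. Reconcile the one-arm cardiac exclusion in section 2.4.4 item 4 with the common exclusion list in section 2.4.3 b. Numbered containers cannot keep the arm hidden while an exclusion depends on it. Which rule applies is for the investigators.

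The cost is packing time, a protocol paragraph and a per-patient emergency code-break. The random list, sample size and visits do not change. Access to a pharmacy and to a placebo that can be matched is an assumption, since the documents mention neither.

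### Removing randomised patients who develop acute kidney injury limits the 6-month eGFR comparison, on the natural reading, to a group defined after treatment starts; the resulting bias can go either way and its size is unknown

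*Combined protocol and SAP*

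**What the plan says.** All references are to the combined protocol and SAP.

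- **Rule (2.4.3 b, Exclusion criteria):** "Any patient will develop acute kidney injury episode at any time of the study will be excluded from the study". Under 2.4.1, patients are randomised once they meet the inclusion criteria, so the rule covers events after randomisation. AKI has no definition.
- **Aim (2.2):** "This study aim is to evaluate whether treatment of hyperuricemia affects renal disease progression".
- **Primary outcome (2.4.5 a):** "To detect effect of treatment of hyperuricemia on eGFR as an objective criterion for assessment of progression of diabetic nephropathy".
- **Assessments (2.4.4):** "At the beginning of the study all patients will be investigated for: serum uric acid, HbA1c and renal function tests including creatinine clearance"; then, in item 5, "eGFR will be done for Assessment of the outcome of the intervention after 6 months". No renal test is scheduled in between. The list is introduced as applying to every patient, and this is not reconciled with the exclusion.
- **Data sources (2.5):** data sheets are also filled "from the recent medical records of the patients". Nothing says that later eGFR values of removed patients would be sought there.
- **Analysis (2.5):** the section covers descriptive summaries, the t test and ANOVA, the software and the significance level. It gives no analysis set, no statement on analysis as randomised, no missing-data rule and no AKI reporting by arm.
- **Sample size (2.4.3 c):** 87 per group, with an allowance for a drop-out "rate of 10%, this will make sample size 96", rounded to 100. AKI removals are not mentioned.

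**The concern.** Randomisation makes the two arms comparable as a whole. It does not make the patients who stay AKI-free comparable, because staying AKI-free is decided after treatment starts and may depend on treatment. Here the event that removes a patient is itself renal and the outcome is renal function, so removal and outcome are likely to be related.

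Two things are at stake. First, an effect of febuxostat on kidney function that runs through AKI, whether harm or benefit, would be left out of the primary comparison. Second, even without lasting damage from AKI, patients prone to AKI may have lower eGFR anyway. Removing different numbers of them from each arm would then create a difference.

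Because AKI is undefined and no renal test is scheduled between the start and 6 months, removal depends on which episodes come to attention and on judgement. Values not collected may not be recoverable later.

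**Working it through.** **1. The plan's own figure.** Inputs from 2.4.3 c: standardised effect 0.43, alpha 0.05, power 80%, and "mean of GFR in the group received Febuxostat Group was 46.7 ± 18.1 and in the placebo group the mean was 42.2 ± 11.5".

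- A two-sided two-sample t test at 0.43 needs 86 per arm by the exact calculation. The stated 87 gives power 80.5%, so the figure is reproduced.
- Pooled SD = sqrt((18.1² + 11.5²)/2) = 15.16.
- Difference implied by 0.43: 0.43 × 15.16 = 6.52 mL/min. The cited means differ by 46.7 − 42.2 = 4.5. That mismatch is a separate matter; 6.52 is used below because it is what the 87 rests on.
- Standard error at 87 per arm = 15.16 × sqrt(2/87) = 2.30.

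**2. Formula for the shift.** In each arm let p be the risk of removal for AKI, and let d be the mean 6-month eGFR of AKI-free patients minus that of AKI patients. The all-randomised mean is the AKI-free mean minus p × d. So, for febuxostat (F) minus placebo (P):

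shift from removal = AKI-free difference − all-randomised difference = pF·dF − pP·dP

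A positive value favours febuxostat. Because d is the observed deficit, it includes both damage from AKI and selection of sicker patients.

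**3. Size.** The documents give none of these inputs. Assumed: p of 2-10% and d of 5-15 mL/min.

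| Case | Calculation | Shift (mL/min) |
|---|---|---|
| Equal risks, equal deficits | d × 0 | 0 |
| Risk gap 1 point, equal deficits | 0.01 × 5 to 0.01 × 15 | 0.05 to 0.15 |
| Risk gap 2 points, equal deficits | 0.02 × 5 to 0.02 × 15 | 0.10 to 0.30 |
| 10% v 2%, equal deficits | 0.08 × 5 to 0.08 × 15 | 0.40 to 1.20 |
| 10% v 2%, unequal deficits | 0.10 × 15 − 0.02 × 5 | 1.40 |
| Equal risk 5%, deficits 10 v 5 | 0.05 × 10 − 0.05 × 5 | 0.25 |

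Signs reverse if the arms swap. A shift of 0.30 is 0.30/2.30 = 0.13 standard errors, and 1.2 is 1.2/2.30 = 0.52.

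**4. Direction.** Neither frequency nor severity alone fixes the sign. With AKI in 6% on febuxostat (deficit 5) and 4% on placebo (deficit 10), the shift is 0.06 × 5 − 0.04 × 10 = −0.10. It goes against febuxostat although AKI is more frequent on febuxostat. With 10% × 5 v 5% × 10, the shift is zero although both differ.

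**5. Chance of a significant result** (true difference 6.52, 87 per arm, two-sided t test):

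| Shift | Rejection rate |
|---|---|
| 0 | 81% |
| −0.30 / +0.30 | 77% / 84% |
| −1.2 / +1.2 | 63% / 92% |

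**6. Limiting cases.**

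- If febuxostat affects neither AKI nor eGFR, the AKI-free groups have the same distribution and the false-positive rate stays at 5%.
- If febuxostat acts only through AKI (10% v 2% or the reverse, deficit 15), the true difference of −1.2 or +1.2 is estimated as 0.
- Selection alone, with no true effect on eGFR: assume AKI odds rise e-fold per SD lower eGFR and risks are 5% on febuxostat v 10% on placebo. A simulation gives a false difference of −0.66. At 5% in both arms it is 0.

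**7. Numbers left.** If AKI removals come on top of 10% drop-out, 100 × 0.90 × 0.98 = 88 to 100 × 0.90 × 0.90 = 81 per arm remain. Power for 6.52 without bias is then 81% to 78%.

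**The case against.** **The rule does not say that these patients leave the analysis.** This is correct as a matter of wording. Exclusion from the study is not literally exclusion from the analysis, and 2.4.4 introduces the 6-month eGFR as something every patient has. But no text keeps an excluded patient in follow-up or in an analysis set. Removal is the natural reading, not an explicit one, and the two sections are at least unreconciled.

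**The sponsor may want chronic progression only.** Section 2.4.3 speaks of chronic kidney disease progression and 2.4.5 of diabetic nephropathy, so setting acute events aside is a possible intention. It does not rescue the comparison, because removal after randomisation can still select different patients in each arm. An AKI-free analysis can be kept as a sensitivity analysis.

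**The effect is small and wholly assumed.** Largely right. The equal-deficit extreme of 1.2 needs a five-fold risk ratio and a deficit of about one SD. After the fix, a true difference of 1.2 would be detected with only about 8% power at 90-100 per arm. AKI counts by arm would reveal more than the primary comparison.

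**Stronger readings to avoid.** A reader might infer that the rule hides harm, or that it favours febuxostat whenever AKI is more frequent or more severe on it. Step 4 shows that this does not follow. A reader might also infer that a low 6-month value could be labelled AKI and dropped. The absence of a definition leaves that open, but nothing in the documents describes it. Nor do the documents show that the trial's result will be materially biased.

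**Conclusion.** The rule is wrong as written and should be changed. Followed on its natural reading, it replaces the all-randomised comparison with one among patients selected by a renal event after randomisation. The bias is pF·dF − pP·dP: zero when the products match, and otherwise in either direction.

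Its size cannot be found from the documents. Under assumed removal risks of 2-10% and deficits of 5-15 mL/min, it is 0.05-0.30 mL/min for a 1-2 point risk gap with equal deficits and at most 1.4 in either direction. That is probably small beside a standard error of 2.3, but the plan does not provide for the data that would show it. The finding therefore rests on the rule and on the absence of any provision to keep these patients, not on a demonstrated large bias.

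**What to change.** - Reword the sentence in 2.4.3 b so that AKI after randomisation does not remove a patient from follow-up or from the primary analysis.
- Obtain the planned 6-month eGFR in all randomised patients where possible, and analyse them in the arm to which they were randomised.
- State the AKI definition used (the sponsor's choice) and report AKI counts by arm.
- State in advance how death, dialysis or a missing eGFR is handled (the method is the sponsor's choice).
- An analysis without AKI patients may be a labelled sensitivity analysis.
- Whether study treatment stops after AKI is a separate clinical decision for the investigators and should not determine inclusion in the analysis.

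**Cost.** Protocol wording, some retention effort, and the already planned eGFR in about 2-10 more patients per 100 under the assumed risks. The outcome SD rises somewhat. At 10% AKI and a mean deficit of 15 it is sqrt(15.16² + 0.10·s² + 0.10 × 0.90 × 15²), where s is the SD of the deficit. This gives 15.8 (s = 0) to 16.5 (s = 15), against 15.2. The standard error is 2.24-2.34 with 100 per arm retained, against 2.26 with 90 after removal. With 10% drop-out as well, it is 2.36-2.46 (90 per arm) against 2.38 (81 per arm). Precision is about the same; the gain is less bias, not more power.

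### Cardiac patients are excluded from the febuxostat group only, so the two groups are no longer comparable by randomisation

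*Combined protocol and SAP*

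**What the plan says.** Section 2.4.1 states that "patients fulfilling inclusion criteria will be randomized to two groups", by a computer-generated list allocating "study drug and placebo in a 1:1 ratio", concealed in sequentially numbered sealed envelopes.

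Section 2.4.3 b lists who may not enter. It begins "Patients with history of hypothyroidism, alcoholism, urinary tract infections, glomerulonephritis, myeloproliferative disorders and gout", goes on to drugs that raise uric acid and to acute kidney injury during the study, and ends "Patients with uncontrolled hypertension will be excluded from the study". Cardiac disease is not on the list.

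The only cardiac rule is in section 2.4.4, item 4 (Intervention), where the drug group is described and the comparator follows in the next sentence without that restriction: "cardiac patients will be excluded from this group. the other group will take placebo pills (placebo group".

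The primary outcome in section 2.4.5 is "To detect effect of treatment of hyperuricemia on eGFR as an objective criterion for assessment of progression of diabetic nephropathy", and eGFR is assessed after 6 months. Section 2.5 plans a Student t test and ANOVA. It names no adjustment for cardiac status and no analysis population.

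**The concern.** Randomisation supports a causal reading of the eGFR difference because eligibility is settled before allocation and is the same for both groups. A criterion that applies to the drug group alone can be enforced only after the assignment is known. Concealing the envelopes does not help, because the selection happens after they are opened.

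Followed as written, the rule removes cardiac patients allocated to febuxostat (or moves them to placebo) and keeps those allocated to placebo. If cardiac patients with diabetes and stage 3 CKD have lower or faster-falling eGFR, which is plausible, the placebo mean is pulled down and febuxostat looks protective even if it does nothing. Nothing in the planned analysis would detect or correct this, and a reader of the result could not tell how much of the difference came from the rule. If removed patients are not replaced, the drug arm also shrinks beyond what the 10% dropout allowance covers.

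**Working it through.** **1. Which patients the rule reaches.** The common list in 2.4.3 b excludes people from the study. The cardiac clause in 2.4.4 excludes them from one group, and grammatically that group is the drug group. No other text extends the clause to placebo. Uncontrolled hypertension is the nearest common criterion, but it is not a general cardiac exclusion.

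**2. The plan's own sample size.** Section 2.4.3 c gives effect size 0.43, alpha 0.05, power 80% and 87 per group.

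- A two-sided comparison of two means needs 85 per group by the normal formula and 86 by the noncentral t. Power at 87 is 80.5%, so the stated 87 is reproduced.
- Dropout: 87 × 1.10 = 95.7, or 96; 87 / 0.9 = 96.7, or 97. The plan says 96 and rounds to 100.
- The same paragraph gives means of 46.7 and 42.2, a difference of 4.5, with SDs of 18.1 and 11.5. The pooled SD is √((18.1² + 11.5²)/2) = 15.16. (4.5/15.16 is 0.30, not 0.43. That is a separate matter and does not affect this point.)

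**3. Bias.** Let f be the cardiac share among randomised patients, and D the amount by which mean 6-month eGFR is lower in cardiac than in non-cardiac patients. Neither is in the documents, so both are assumptions. Let m be the non-cardiac mean, and suppose the drug has no effect.

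- Febuxostat group, cardiac patients removed: m
- Placebo group, cardiac patients kept: m − f × D
- Expected difference: f × D, in favour of febuxostat when D > 0

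**4. False-positive rate.** Inputs: no drug effect, SD 15.16, 100 randomised per arm, 10% dropout, cardiac patients removed from the drug arm and not replaced. The evaluable numbers are then 90 × (1 − f) on febuxostat and 90 on placebo. Rejection is computed from the noncentral t with noncentrality f × D / [15.16 × √(1/n₁ + 1/n₂)].

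| f | D | Bias f × D | Share of 4.5 | n drug / placebo | Rejection (nominal 5%) | Share of rejections favouring febuxostat |
|---|---|---|---|---|---|---|
| 10% | 3 | 0.3 | 7% | 81 / 90 | 5.2% | 65% |
| 20% | 5 | 1.0 | 22% | 72 / 90 | 7.0% | 87% |
| 30% | 5 | 1.5 | 33% | 63 / 90 | 9.2% | 94% |
| 30% | 8 | 2.4 | 53% | 63 / 90 | 16% | 99% |
| 40% | 8 | 3.2 | 71% | 54 / 90 | 23% | nearly all |

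For example, with f = 20% and D = 5 the standard error is 15.16 × √(1/72 + 1/90) = 2.40, and the noncentrality is 1.0/2.40 = 0.42. A simulation of 40,000 runs gave 6.6%, 9.0%, 15% and 22% for the last four rows, which agrees within about one percentage point.

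**5. What happens to the excluded patient matters, and the plan does not say.**

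- If replaced to fill the drug arm (90 evaluable per arm), the bias is unchanged and rejection is 7.2%, 10% and 29% for (20%, 5), (30%, 5) and (40%, 8).
- If moved to placebo, the cardiac share there becomes 2f/(1 + f). The bias is 2fD/(1 + f) = 1.7, 2.3 and 4.6, and rejection is 11%, 16% and 45%.

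**6. Power.** If patients are removed without replacement, the drug arm has 81, 72, 63 or 54 evaluable patients for f = 10, 20, 30 or 40%, against the 87 required. Power at the plan's 0.43 is then about 80, 78, 74 or 70% (normal approximation).

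**7. After the fix.** With the same exclusion before randomisation in both arms, both group means equal m under the null. The expected bias is 0, the false-positive rate returns to 5%, and 87 per group (100 with the allowance) stands.

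**The case against.** The strongest defence is that this is loose drafting. A cardiac safety restriction written beside the drug may have been meant for every candidate at screening, in a form that also labels the trial a case-control study. That is possible, but the text does not say so: it uses different wording from the common list and describes placebo separately. Staff who follow it would apply it to one arm. If both arms were intended, the correction costs nothing.

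Other objections concern size, and several stand:

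- Bias needs an association between cardiac status and 6-month eGFR. If D is zero there is none, and if the endpoint is analysed as change, D is the difference in change and may be smaller.
- At f = 10% and D = 3 the inflation is trivial. The top case assumes 40% cardiac patients who differ by 8 units in a trial whose eGFR entry window runs only from 31 to 59. It is an upper illustration, not an expectation.
- The arm falls below 87 only if excluded patients are not replaced. The plan promises 100 per group, and the power loss is modest even without replacement.
- Non-cardiac patients remain comparable between arms. If the baseline history records cardiac disease, dropping cardiac placebo patients at analysis could restore symmetry. That rescue is not planned, and it would depend on a term, cardiac patients, that the plan does not define.

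None of this makes a one-arm exclusion acceptable.

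**Conclusion.** The concern holds. As written, the plan applies an eligibility criterion to one randomised arm after allocation, which is a structural error in the primary comparison and not a missing detail. The direction and size of the bias cannot be determined from the documents. Under the assumed inputs it ranges from negligible (0.3 units, 5.2% false positives) through moderate (1.0 to 1.5 units, about 7 to 9%) to large (3.2 units, about 23%) when cardiac disease is common and strongly related to eGFR; moving patients to placebo would make it worse. These figures assume no drug effect, a common SD of 15.16, 10% dropout, and lower eGFR in cardiac patients. The rule must be corrected before enrolment, because the imbalance is hard to repair afterwards.

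**What to change.** Delete the cardiac clause from section 2.4.4, item 4. Add cardiac disease to section 2.4.3 b, with a definition of which conditions count, as a criterion checked for every candidate at screening before the envelope is opened and applied identically to both groups. State in section 2.5 that everyone randomised is analysed in the group assigned.

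The cost is a small protocol edit with no extra procedure and no change to the stated sample size. More candidates must be screened: filling 200 places takes 200/(1 − f) otherwise eligible candidates, or about 222, 250, 286 or 333 for f = 10, 20, 30 or 40%. The burden is small where the bias is small, and larger where cardiac disease is common and the correction matters most.
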